The purpose of the research project is to utilize a participatory research approach in partnership with three communities to test the effectiveness of an existing intergenerational culturally adapted curriculum. With Native American Research Centers for Health (NARCH) funding, the FL/CP was co-created and pilot tested by CBPR partnerships between the University of New Mexico Center for Participatory Research (UNM-CPR) and three tribal communities, the Pueblo of Jemez, Ramah Navajo and Mescalero Apache. These existing long-term partnerships have co-produced the tribal-specific FL/CP curriculums in Pueblo, Navajo and Apache versions. This CBPR project supports the rigorous testing of the intergenerational Family Listening/ Circle Program as a culturally centered and evidence based prevention program that has produced promising

preliminary data in reducing substance abuse risk factors for elementary school children. This grant will not only aggregate sufficient numbers to test FL/CP effectiveness but also illustrate how an intervention can disseminate and share “evidence- based processes and components” and also integrate understandings from implementation and CBPR science, that culture and community context must be integrated for the intervention to be effective and to generate community ownership. The R01 specific aims over a five year period are as follows:

Aim One:

Rigorously test the effectiveness of the Family Listening/Circle Program (FL/CP), with a comparative longitudinal design within and across three small tribal communities, with 4th graders to prevent substance abuse initiation disparities and to strengthen family well-being. Through a quasi- experimental longitudinal design, we will test effectiveness of the FL/CP prevention program with an intervention group of 4th graders as compared with other 4th graders, both within and across the three tribes. Quantitative pre-, post-, 6- month and 1 year –post measures of substance abuse risk and protective factors will be triangulated with qualitative data, also comparing children and parent responses on psycho- social factors, family communication and cultural connectedness. Process evaluation will assess satisfaction, quality, and fidelity to both core evidence and specific cultural curriculum components.

Aim Two:

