Leaders, managers, educators, and/or staff. For the third aim of the grant, in the first program year, the UNM and community TRTs will conduct a review of community organizations and prevention and youth programs in the community and at schools. From this review of programs, the pool of managers and educators will be identified.

Community/traditional leaders may not be affiliated with programs therefore we will rely on the community knowledge and connections of the Tribal Research team members to recruit these leaders. Starting in year 1 and continuing through year 5, TRT members will recruit those identified by phone or face-to-face communication. The consent process as detailed above will occur immediately prior to the individual interview. Potential participants will be contacted and interviews will be conducted during the fourth quarter of each program year. The described recruitment process is the preferred method by the respective TRTs because it ensures a) involvement with this study is entirely participatory and voluntary and b) an understanding of the research involved by potential participants is obtained and discussed to satisfaction of TRT members, with UNM research team members present and available as necessary.

8) Study Timelines

Attached updated study timeline (see Attachment B)

9) Study Endpoints

Our final endpoint will be the collection in year 5 of the one-year post-test of the final program implementation groups in year 4. A potential reason to terminate the study would be when there are no voluntary family participants.

10) Research Setting

Describe the sites or locations where your research team will conduct the research.

The Family Listening/ Circle Program will be conducted in three tribal communities in New Mexico. The program is a dinner program with four facilitators and 12 families (child/parent/invited elders) held in tribal facilities, such as a school, a library, an

(09.22.2014)

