The research team will log onto the secure password protected laptop to provide access for the adult participant to take the self-administered pre-web-based survey instrument. For the child participant, a local TRT or UNM research team member will again log onto the secure password protected laptop to administer the pre-web-based survey instrument by reading aloud each question to the child, who will have the laptop with the web-based survey to record each response directly onto the web-based survey behind a desk-top partition, assuring privacy. Once the adult and child pre- web-based surveys are completed the research team member will sign out of the program and shut down the laptop. The consent forms will be collected and placed in a separate sealed envelope and will be transported to UNM in Albuquerque and placed in a different locked filing cabinet in the same locked office of the PI for three years, after which time they (consent forms) will be destroyed according to university procedures in the destruction of hard copies of research documents.

The administration of the post-survey will be conducted at the completion of the twelve week two-hour sessions of the FL/CP prevention/intervention program, and 1yr later and will follow the same steps taken in the administration of the pre-survey as outlined above for both the adult and child participant.—A comparison between pre/post and one year post survey will be conducted by t-testing of comparisons. Findings with statistical significance will be reported and an executive summary will be included. The research team will utilize a participatory approach and engage the tribal research team in the interpretation of the initial findings. Data will be interpreted by the UNM and Tribal Research Teams to ensure cultural appropriateness and reflection of the lived experience of community partners. Dissemination of findings for each community will be based on recommendation by the tribal research team. Past research experience with other tribal communities recommended the preparation of powerpoint slides with findings and brief executive summaries to be shared with tribal leadership and program staff.

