This R01 therefore: 1) supports multilevel understanding and assessment of the FL/CP prevention effectiveness through a quasi-experimental comparison between intervention and comparison children, with triangulation of quantitative and qualitative impact and process measures, and assessment of both core evidence-based and specific cultural components; 2) strengthens research skills of our tribal colleagues as co-researchers building upon research capacities gained from previous CDC and NARCH funded projects; 3) supports a within-tribe longitudinal (pre-post, 6-month post, and 1-year post) that compares program impacts on 4th grade children, their parents and families; and 4) enables an aggregated sample for testing FL/CP effectiveness with sufficient numbers to achieve statistical significance, given effect sizes for preliminary data; and as a scientific inquiry into the role of CBPR in translational research to reduce disparities in Indian country.

As Cook and Campbell (1979) note, there are a wide variety of factors that make the use of randomization procedures in group designs difficult to impossible, especially in field research settings. In the present case, there are a number of factors at work that make the randomization of participants to either an intervention or usual and customary treatment group not feasible. First, the tribal communities that are participating in the proposed

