project are small and close-knit, characterized by highly interwoven social networks [Cook & Campbell, 1979]. As a result, randomly assigning some children and families to the intervention group and not others is problematic because doing so would likely be socially disruptive. Second, the employment of randomization procedures in this setting implies a level of outside political control that is not achievable in tribal communities. These communities have histories of disadvantage and discrimination, and decisions are usually politically closed to those outside the community, research groups included. Third, the norm of collective equity and CBPR processes which honor tribal voice is prominent and strong, and randomization procedures can mitigate against the ethical responsibility to work towards tribal ownership and sustainability once the grant ends [Buchanan, Miller, & [name], 2007]. We propose therefore the use of a two arm non-equivalent control group design with pretest, immediate post- test, and 12 month follow-up assessment points (see Table 2 below). Among quasi-experimental designs that could be employed, this design carries several advantages over other designs in being able to infer causality [Cook & Campbell, 1979], and we shall follow data analysis procedures recommended by Cook and Campbell concerning this design. One advantage of this design is that it allows for a more meaningful analysis of the impact of the FL/CP intervention by a comparison of the intervention group with the usual and customary comparison group, an advantage not possible with single-group over time designs. Second, the design provides an analysis of diffusion effects (i.e. the potential influence of the intervention on the comparison group over time). Given the tight social networks and small number of interconnected families in the three participating communities, we expect some degree of program diffusion in the comparison group families. We will employ analysis procedures to examine this potential diffusion effect (see below in Aim 3).

Study Personnel – N/A

Location – N/A

Informed Consent – N/A

Procedures – N/A

22) Sharing of Results with Subjects/Incidental Findings

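### Aim One names no primary outcome, time point, contrast or error control, so effectiveness could be claimed on whichever comparison proves significant

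*Combined protocol and SAP*

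**What the plan says.** **Outcomes and comparisons.** Section 3, Aim One, lists substance abuse risk and protective factors first. It then plans qualitative triangulation, "also comparing children and parent responses on psycho- social factors, family communication and cultural connectedness". The comparison of fourth graders is to be made "both within and across the three tribes". No construct, respondent or level is put first.

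**Time points.** Aim One and the opening list in Section 21 include a 6-month assessment. Table 2 in Section 6, the survey schedule in Section 14 and the design statement later in Section 21 have only pre-test, immediate post-test and one-year follow-up.

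**Endpoint.** Section 9 states: "Our final endpoint will be the collection in year 5 of the one-year post-test". This is the end of fieldwork, not an outcome variable.

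**Analysis.** Section 14 (Quality assurance plan) states: "A comparison between pre/post and one year post survey will be conducted by t-testing of comparisons". Section 21 describes assessing impact "by a comparison of the intervention group with the usual and customary comparison group" and says "we shall follow data analysis procedures recommended by" a cited text on quasi-experimental designs. It also says that the study "enables an aggregated sample for testing FL/CP effectiveness with sufficient numbers to achieve statistical significance, given effect sizes for preliminary data". It gives no alpha, power or effect size, and does not say which outcome is meant.

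**Reporting.** Section 14 states: "Findings with statistical significance will be reported and an executive summary will be included". Section 22 promises the communities all of their own results in aggregate. Section 25 provides means, medians, standard deviations and effect sizes to each Tribal Research Team (TRT). Neither attaches a significance condition. Section 22 also plans national presentations and publications of the three-community results, without saying how complete they will be.

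**The concern.** An effectiveness trial needs one question whose false-positive rate is set in advance. Here the outcome, respondent, time point and level of comparison are all open, and the only operational rule in the text is to run t-tests and report the significant findings. Any one significant comparison could then be presented as the answer to Aim One, and the chance of that happening without a program effect rises with the number of comparisons.

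Section 2 states the intention to disseminate the program within Indian Country as a best practice, so other tribes could act on a chance result. The choice cannot be made credibly once the data have been seen.

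**Working it through.** **1. The plan's own figure.** Section 6 gives 48 participants x 3 tribes x 4 waves = 576, which reproduces. It is a recruitment total. With no alpha, power or effect size stated, there is no power or error calculation to reproduce.

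**2. How many tests?** The document does not say, so three counts are assumed. All use pooled program-versus-comparison tests only and two follow-ups (post-test and one year).
- Children only: 3 domains (psycho-social factors, family communication, cultural connectedness) x 2 follow-ups = 6.
- Children and parents: 3 x 2 respondents x 2 = 12.
- Adding substance abuse risk and protective factors as a fourth construct: 4 x 2 x 2 = 16.

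**3. Chance of at least one false positive.** Assumptions: two-sided 0.05 per test, no program effect, and equally correlated normal test statistics with correlation r.
- Independent tests, either direction: 1 − 0.95^m. For m = 6, 1 − 0.95^6 = 0.265; for m = 12, 0.460; for m = 16, 0.560.
- Independent tests, favouring the program: 1 − 0.975^m. For m = 6, 0.141; for m = 12, 0.262; for m = 16, 0.333.
- Correlated tests: one minus the integral, over a shared normal component u, of φ(u) × [Φ((1.96 − u√r)/√(1−r)) − Φ((−1.96 − u√r)/√(1−r))]^m. The lower term is dropped when only results favouring the program count.

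| Tests | Either direction, r = 0.7 / 0.5 / 0.3 / 0 | Favouring the program, r = 0.7 / 0.5 / 0.3 / 0 |
|---|---|---|
| 1 | 5.0% at any r | 2.5% at any r |
| 6 | 16.4 / 20.7 / 24.1 / 26.5% | 8.2 / 10.4 / 12.2 / 14.1% |
| 12 | 23.2 / 31.9 / 39.7 / 46.0% | 11.6 / 16.0 / 20.2 / 26.2% |
| 16 | 26.4 / 37.4 / 47.6 / 56.0% | 13.2 / 18.8 / 24.4 / 33.3% |

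**4. What the counts leave out.** If the 6-month assessment takes place, the last count becomes 4 x 2 x 3 = 24, and the either-direction range is about 31% to 71%. Separate tests within each tribe would add more.

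**5. What pre-specification buys.** With 144 children per group, 80% power, complete data and independent observations (all assumed), the detectable difference is (z for alpha + 0.842) × √(2/144). One test at 0.05 gives (1.960 + 0.842) × 0.1179 = 0.33 SD. Sixteen tests under Bonferroni (alpha 0.05/16 = 0.0031) give 0.45 SD. Naming one primary test controls the error without that loss.

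**The case against.** **The reporting sentence is weaker than it looks.** A reader might infer that non-significant results will be withheld. The documents do not support that. The sentence does not say that only significant findings will be reported, and it leads into text about TRT interpretation, slides and executive summaries, so it may describe a summary product. Sections 22 and 25 promise community results and effect sizes without a significance condition. This objection stands. What remains is that no sentence promises complete reporting of the pooled results in presentations and publications. For the same reason, calculations of how far estimates would be inflated if only significant ones appeared do not belong in the case.

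**The plan is less open than the larger counts suggest.** Aim One compares fourth graders with other fourth graders, and Section 21 refers to intervention and comparison children. That favours a child outcome and the pooled contrast, which is why a child-only count is included. It is not decisive, because Section 21 also lists impacts on parents and families, and no child outcome or time point is chosen.

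**The details may lie elsewhere.** This is a protocol written for an ethics board. It relies on a cited methods text and points to Aim 3 analysis text that is not reproduced. That limits the finding to this document. Even so, a general methods text cannot choose this trial's primary outcome or time point.

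**Conclusion.** The point holds for this document. No primary outcome, time point or contrast is named, no alpha or multiplicity rule is given, the 6-month assessment is inconsistent, and the t-tests of Section 14 are not reconciled with the procedures promised in Section 21. An effectiveness claim made under these rules would have no controlled error rate.

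The plausible size runs from about three times the nominal 5% (16.4%, six child-only tests, correlation 0.7) to about eleven times (56.0%, sixteen independent tests). Counting only results that favour the program, it runs from 8.2% to 33.3% against a nominal 2.5%. These figures rest on assumed test counts, two-sided 0.05 and equal correlation. They show the scale of the problem and do not predict this trial's error rate.

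Selective reporting is a secondary wording risk, limited to pooled presentations and publications. It is not a stated plan to withhold results. Because a positive result is meant to support wide dissemination, the primary test should be fixed before any outcome analysis.

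**What to change.** 1. **Section 9.** Before analysis, the investigators and TRTs name one primary child outcome already being collected (or a small ranked set with error control), its time point, and the pooled program-versus-comparison contrast with its alpha. They reconcile whether there is a 6-month assessment, and state whether the t-tests of Section 14 or the recommended procedures of Section 21 apply to that contrast. If another study document already fixes any of this, cite it here.
2. **Other outcomes.** Treat them as secondary with Holm or false discovery rate control, or label them exploratory. Give within-tribe results as estimates with intervals.
3. **Section 14.** Replace the reporting sentence with: *all pre-specified outcomes will be reported with estimate and 95% CI whatever the p-value*. State that this covers the pooled publications, in line with Sections 22 and 25.

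**Cost.** The change is to wording only, with no new data collection. It needs TRT agreement and sign-off from the reviewing boards, and fewer secondary results can be called significant. It does not address bias from self-selected enrolment (Section 7), which has to be handled separately.
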